4.2.10. CARDIFF WOUND IMPACT QUESTIONNAIRE (CWIQ)

The CWIQ is a measure designed to assess the impact of ulcers on patient health-related quality of life (HRQoL). There is a total of 3 domains:

- Social life (14 items, graded on a 5-point Likert scale)
- Well-being (7 items, graded on a 5-point Likert scale)
- Physical symptoms and daily living (24 items, graded on a 5-point Likert scale)

In addition, there are Overall Quality of Life questions (2 items graded on a 11-point Likert scale).

The CWIQ will be completed by the subject at Day 0, Day 120 (4 months) and Day 210 (7 months). The score data will be summarized based on the CWIQ scoring instructions. The questionnaire can be found in Appendix 8.

4.2.11. INJECTION SITE REACTION ASSESSMENT

Local injection sites reactions will be assessed on Day 0 post injection, Day 14 pre and post injection, Day 28 pre and post injection, Day 42 pre and post injection, Day 60, and at each wound assessment/dressing change visit after the first injection visit and prior to Day 60. Injection site reactions will be reported on the Injection Site Adverse Event form. The location (calf area) and temporal relationship to the most recent study injections will determine whether the event is an injection site reaction or adverse event.

Table 6. Injection Reaction Assessment

ADVERSE EVENT	GRADE 1	GRADE 2	GRADE 3	GRADE 4	GRADE 5
Injection site reaction	Pain, itching, erythema	Pain or swelling, with inflammation or phlebitis	Ulceration or necrosis that is severe; operative intervention indicated		
Ulceration		Superficial ulceration < 2 cm size; local wound care; medical intervention indicated	Ulceration ≥2 cm size; operative debridement, primary closure or other invasive intervention indicated (e.g., hyperbaric oxygen)	Life-threatening consequences; major invasive intervention indicated (e.g., complete resection, tissue reconstruction, flap, or grafting	Death

Adverse Event	GRADE 1	GRADE 2	GRADE 3	GRADE 4	GRADE 5
Allergic reaction / hypersensitivity	Transient flushing or rash; drug fever < 38°C (<100.4°F)	Rash; flushing; urticaria; dyspnea; drug fever ≥38°C (≥100.4°F)	Symptomatic bronchospasm, with or without urticaria; parenteral medications(s) indicated; allergy-related edema/ angioedema; hypotension	Anaphylaxis	Death

5. EVALUATION OF ADVERSE EVENTS

5.1. **DEFINITIONS**

An Adverse Event (AE) is the development of an untoward medical occurrence or the deterioration of a pre-existing medical condition following or during exposure to an investigational product, whether or not considered causally related to the product.

An untoward medical condition can be symptoms (e.g., nausea, chest pain), signs (e.g., tachycardia, enlarged liver) or clinically significant abnormal results of an investigation (e.g., laboratory findings, electrocardiogram).

Conditions or diseases that are chronic but stable should not be recorded as an AE. Changes in a chronic condition or disease that are consistent with natural disease progression are NOT considered AEs and also should not be recorded in the AE form of the electronic data capture system (EDC). These medical conditions should be adequately documented on the appropriate form of the study EDC (relevant medical history and/or physical examination). However, medical conditions present at enrollment that worsen in intensity or frequency in a manner inconsistent with the natural course of the disease during the treatment or post-treatment periods should be reported and recorded as AEs.

An **adverse reaction** means any adverse event caused by a drug. Adverse reactions are a subset of all suspected adverse reactions for which there is reason to conclude that the drug caused the event.

Suspected adverse reaction means any adverse event for which there is a reasonable possibility that the drug caused the adverse event. For the purposes of IND safety reporting, 'reasonable possibility' means there is evidence to suggest a causal relationship between the drug and the adverse event. A suspected adverse reaction implies a lesser degree of certainty about causality than adverse reaction, which means any adverse event caused by a drug.

A serious adverse event (SAE) is any untoward medical occurrence which:

- Results in death;
- Is life-threatening;
- Requires inpatient hospitalization (admission to hospital with a stay > 24 hours) or prolongation of hospitalization which is not specifically required by the protocol or is elective. Hospitalization for elective treatment of a pre-existing condition that has not worsened is not considered to be an AE. Hospital admissions or surgery planned before any study drug is administered are not to be considered AEs unless there is unexpected deterioration of the subject's condition after study drug treatment (e.g., surgery must be performed earlier than planned).
- Results in permanent impairment of a body function or permanent damage to a body structure; or
- Requires medical or surgical intervention to preclude permanent impairment of a body function or permanent damage to a body structure.

Additionally, important medical events that may not result in death, be life-threatening or require hospitalization may be considered SAEs when they jeopardize the subject or require medical or surgical intervention to prevent one of the serious outcomes listed above. Examples of such medical events include: allergic bronchospasm requiring intensive treatment in an emergency room or at home, blood dyscrasias or convulsions that do not result in inpatient hospitalization or the development of drug dependency or drug abuse. Medical and scientific judgment must be exercised when classifying events as serious.

Life-threatening means that the subject is, in the view of the investigator, at immediate risk of death from the AE as it occurred. It does not include an AE which, had it occurred in a more serious form, might have caused death.

Persistent or significant disability/incapacity means that the event resulted in permanent or significant and substantial disruption of the subjects' ability to carry out normal life functions.

An unexpected AE is an AE, the nature or severity of which is not consistent with the applicable product information (e.g., Investigator Brochure for an unapproved product). Expected means that the event has been previously observed with the test article and is identified and/or described in the applicable product information. It does not mean that the event is expected with the underlying disease(s) or concomitant medications. It is expected that certain disease states will have reoccurring adverse events some of which may be considered expected over time.

5.2. ASSESSMENT OF ADVERSE EVENTS (AES)

All AEs, regardless of severity, occurring following the first study drug administration and the 7-month follow-up visit of the study by a subject must be recorded in the AE form of the EDC. Any events occurring before the injections will be added to the medical history. This will include the following information:

- Description of the AE
 - Every effort must be made to report the underlying condition or unifying diagnosis for the event. In order to avoid vague, ambiguous or colloquial expressions, the AE should be recorded in standard medical terminology rather than the subject's own words when possible. Signs and symptoms that are considered unrelated to an encountered syndrome or disease should be recorded as individual AEs (e.g., if congestive heart failure and severe headache are observed at the same time, each event should be recorded as an individual AE. In addition, AEs occurring secondary to other events (e.g., sequelae) should be identified by the primary cause (i.e., a "primary" AE, if clearly identifiable, generally represents the most accurate clinical term to record; events occurring secondary to the primary event should be described in the narrative description of the case [e.g., orthostatic hypotension → fainting and fall to floor → head trauma → neck pain; the primary AE is orthostatic hypotension]).
- Date of onset
- Duration
- Frequency
- Severity
- Seriousness (yes/no)
- Treatment
- Outcome
- Relationship to study medication, injection procedure and/or underlying disease

All AEs and SAEs must be followed until resolution, or the condition stabilizes. The Investigator is responsible to ensure that follow-up includes any supplemental investigations as may be indicated to elucidate as completely as possible the nature and/or causality of the AE or SAE. This may include additional laboratory tests or investigations, histopathological examinations, or consultation with other health care professionals. The Sponsor or its designee may request that the Investigator perform or arrange for the conduct of supplemental measurements and/or evaluations.

5.2.1. AE CAUSALITY

The study investigator will determine whether an AE is related or unrelated to study medication, the procedure (IM injection) and / or the underlying disease using the following criteria:

Not related: An adverse event that is not related to the use of the test article or administration procedure.

Possibly related: An adverse event that might be due to the use of the test article or administration procedure. An alternative explanation, e.g., concomitant study product(s), concomitant disease(s), is inconclusive. The relationship in time is reasonable; therefore, a causal relationship cannot be excluded.

Probably related: An adverse event that might be due to the use of the test article or administration procedure. The relationship in time is suggestive. An alternative explanation is less likely, e.g., concomitant drug(s), concomitant disease(s).

Definitely related: An AE that is due to the use of the test article or administration procedure. The event cannot be reasonably explained by an alternative explanation – e.g., concomitant drug(s), concomitant disease(s).

5.2.2. AE INTENSITY

The worst intensity of the AE/SAE will be reported using the following criteria:

Mild: The AE is noticeable to the subject but does not interfere with

routine activity.

Moderate: The AE is discomforting and interferes with routine activity.

Severe: The AE significantly limits the subject's ability to perform

routine activities despite symptomatic therapy.

5.3. REPORTING/RECORDING OF AES

Throughout the course of the study, all efforts will be made by the investigator to remain alert to possible AEs. The first concern will be the safety of the subject, and for providing appropriate medical intervention. The period of observation for collection of AEs occurs following the first study drug administration until the 7-month follow-up visit. Any AE should be recorded in the EDC. Any events occurring before the injections will be added to the medical history.

5.4. REPORTING / RECORDING OF SAES

5.4.1. INVESTIGATOR'S RESPONSIBILITY

SAEs will be recorded following the first study drug administration through the 7-month follow-up visit. Any serious adverse event that occurs during this investigation, whether or not related to the study medication, must be reported as soon as possible but no later than 3 working days after the investigator first learns of the event to the Sponsor and CRO. However, if the EDC is inaccessible, then in order to report an SAE within the required timeframe, a paper SAE form must be used and submitted to

Once the EDC becomes accessible, the data must be entered into EDC as per standard procedure. If secondary or tertiary diagnoses occur concurrent to the primary SAE (e.g., during a hospitalization period), these additional diagnoses should be recorded in the follow-up reports to the index SAE.

Each SAE must be followed with appropriate medical management until resolved or assessed as chronic or stable regardless of whether or not, in the opinion of the Investigator, the event is thought to be related to the study medication.

The Investigator will be required to provide complete information (including the Investigator's opinion of the relationship of the SAE to the study medication) concerning each SAE to the CRO and Sponsor within 5 working days of first learning of the event. The investigator or designee will provide copies of related source documentation such as results/reports, hospitalization records, and other relevant information involving the SAE.

In the event of an SAE leading to hospitalization, every effort will be made by the investigational site to obtain medical records, including a hospital discharge summary. In the event of a fatal AE, documentation of any available postmortem findings, including autopsy, will be provided to the Sponsor or their designee. In any event, the Investigator will provide a narrative summary of circumstances/events related to the death, and cause of death, if known.

The Investigator must comply with the applicable local regulatory requirements related to the reporting of SAEs to regulatory authorities and the Institutional Review Board (IRB), and Institutional Biosafety Committee (IBC) if applicable. Upon receipt from the Sponsor of an initial or follow-up IND Safety Report or other safety information, the Investigator must promptly notify his or her IRB, and IBC (if applicable).

5.4.2. Sponsor's Responsibility

All AEs and SAEs will be reported on an annual basis to FDA in accordance with the IND regulation (21 CFR Part 312). Per the 2010 FDA Guidance Document for Industry and Investigators "Safety Reporting Requirements for INDs and BA/BE Studies," events categorized as 'possibly' or 'probably' related will be treated as 'suspected adverse reactions.' Events categorized as 'definitely' related will be treated as an 'adverse reaction.'

All serious, unexpected adverse reactions and suspected adverse reactions will be reported to FDA and to all participating investigators as an IND Safety Report within 15 calendar days of the event after the Sponsor determines that the suspected adverse reaction qualifies for reporting (21 CFR §312.32). Any unexpected fatal or life-threatening AEs will be reported to the Agency within 7 calendar days after the Sponsor's initial receipt of the information.

The Sponsor will notify all participating investigators of any new safety information that alters the current risk-benefit assessment of the study medication or that would be sufficient to consider changes in VM202 administration or in the overall conduct of the trial.

6. STATISTICAL METHODS

6.1. SAMPLE SIZE CALCULATION

The sample size for the primary efficacy endpoint is calculated based on the hypothesis for the primary efficacy endpoint. The primary study endpoint is the proportion of subjects with a target wound closure at 4 months.

The statistical hypotheses for the first primary efficacy endpoint are:

 H_0 : $P_t = P_c$ versus H_a : $P_t \neq P_c$

where P_t and P_c are the proportions of subjects with a target wound closure by the 4-month follow-up for the VM202 and placebo groups, respectively.

The hypothesis testing will be at two-sided 0.05.

Based on prior VM202 studies, the percentage of subjects achieving complete wound closure by the 4-month (i.e., 4-month responder rate) for VM202 (treatment arm) is assumed to range from 50% to 60%, and that for the Placebo group is assumed to range from 20% to 30%. Table 7 below summarizes the statistical power for a sample size of 200 VM202 and 100 Placebo subjects based on Fisher's exact test with a two-sided significance level of 0.05 for the statistical hypothesis.

Table 7. Statistical power by estimated responder rates for Treatment (p_t) and Control (p_c) arms

2100022020 (47) 0220 0022020 (46) 02220						
Pt	рc	Statistical Power				
0.50	0.20	>.999				
0.50	0.25	0.985				
0.50	0.30	0.898				
0.55	0.20	>.999				
0.55	0.25	0.999				
0.55	0.30	0.982				
0.60	0.20	>.999				
0.60	0.25	>.999				
0.60	0.30	0.998				

Except for the assumption of $p_t = 0.50$ and $p_c = 0.30$, the statistical power for all assumptions of p_t and p_c is > 0.95. For the assumption of $p_t = 0.50$ and $p_c = 0.30$, the statistical power is about 90%.

6.2. Analysis Population

6.2.1. Intent-to-Treat Population (ITT)

This subset includes all subjects who are randomized. All baseline characteristics will be summarized based on ITT. Subjects in the ITT will be analyzed according to

original treatment assignment, regardless of actual treatment received. The primary analyses of the primary efficacy endpoint will be based on this ITT population.

6.2.2. SAFETY POPULATION

The safety analysis population will contain all subjects who are randomized and receive at least one study injection. Subjects will be grouped according to their actual treatment received, not according to their randomization assignment (as randomized). Subjects treated with any VM202 dose will be grouped in the VM202 group; subjects treated without any VM202 will be grouped in the placebo group.

6.2.3. MODIFIED ITT (MITT) POPULATION

The mITT population includes all subjects randomized who meet the following:

- Received any study drug injections
- Had at least one post-baseline wound assessment
- Have no safety or efficacy parameter results prior to dosing on Day 0 that would have made the subject ineligible for participation if the results had been known or disclosed at Screening. This determination will be made in a blinded fashion by the Clinical Data Review Committee (CDRC, members to be determined) prior to analyses.

Subjects will be grouped based on the randomly assigned treatments, not the actual treatment received. The mITT population will be used in the sensitivity analyses for the primary endpoint.

6.2.4. PER PROTOCOL (PP) POPULATIONS

6.2.4.1. PP1

The first Per Protocol (PP1) population is a subset of mITT. It includes all mITT subjects who meet the following criterion:

• Have not used the protocol-specified prohibited concomitant medications or treatments such as COX-2 inhibitor drug(s) or non-specific COX-1/COX-2-inhibiting nonsteroidal anti-inflammatory drugs (NSAIDs), anti-VEGF agents (e.g., Lucentis®, Avastin®, Eylea®), steroids (except inhaled steroids or ocular steroids), Regranex® gel (becaplermin), larval debridement, skin substitutes (e.g., Dermagraft®, Apligraf®), hyperbaric oxygen therapy, hydrotherapy, negative pressure wound therapy, or electrical stimulation therapy which may affect the wound healing. The use and effect of protocol-specified prohibited concomitant medications will be determined by the CDRC in a blinded fashion prior to analyses.

6.2.4.2. PP2

The second Per Protocol population is a further subset of the mITT. It includes all subjects in the first PP population who also meet all of the following criteria:

- Meets major protocol eligibility criteria determined by the CDRC in a blinded fashion prior to analyses
- Received all injections based on the randomized treatment.
- Maintained standard of care for their wounds for the duration of the study, as follows:
 - o Surgical debridement of necrotic tissue or devitalized tissue
 - Use of appropriate off-loading when ambulating
 - o Maintenance of moist wound environment
- Additional criteria, if any, established by the CDRC before unblinding of the randomization code.

The PP populations will be used in the sensitivity analyses for the primary efficacy endpoint.

6.3. STUDY ENDPOINTS

6.3.1. PRIMARY ENDPOINT

The primary study endpoint is the proportion of subjects with a target wound closure by the 4-month follow-up. Complete wound closure is defined as skin reepithelialization without drainage or dressing (primary endpoint), confirmed at a second scheduled or unscheduled visit two weeks $(14 \pm 5 \text{ days})$ later (secondary endpoint). Active and placebo arms will be compared to determine treatment effect.

6.3.2. OTHER ENDPOINTS

Other exploratory endpoints will include:

- Time to complete wound closure of foot ulcer
- Proportion of subjects with a target wound closure prior to or at 7 months
- Percent change in wound volume at 2 months, 2.5 months, 3 months, 4 months, and 7 months
- Percent change in wound perimeter, area and wound depth at 2 months, 2.5 months, 3 months, 4 months, and 7 months
- Proportion of subjects with formation of new ulcers on the target foot at 2 months, 2.5 months, 3 months, 4 months, and 7 months
- Time to the major amputations
- Time to the minor amputation
- Change in ABI at 4 months, and 7 months
- Change in TBI at 4 months, and 7 months
- Change in TcPO₂ at 4 months, and 7 months

Change in each domain score (quality of life, social life, well-being, physical symptoms and daily living) of CWIO from Day 0 at 4 months and 7 months

6.3.3. SAFETY

Safety analyses in this study will evaluate the safety profile of VM202, as compared with control. No formal statistical testing will be conducted for the safety analyses. All subjects in the safety subset will be included in these analyses. Subjects will be grouped by treatment received. All summaries will be derived based on available data. No imputation will be performed for missing values.

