1. INTRODUCTION

This document outlines the statistical methods to be implemented during the analyses of data collected within the scope of Helixmith Co., Ltd. (formerly ViroMed Co., Ltd.) Protocol VMNHU-003/I [A Phase III, Double-Blind, Randomized, Placebo-Controlled, Multicenter Study to Assess the Safety and Efficacy of VM202 to Treat Chronic Nonhealing Foot Ulcers in Diabetic Patients with Concomitant Peripheral Arterial Disease (PAD)]. The purpose of this plan is to provide specific guidelines from which the analysis will proceed. Any deviations from these guidelines will be documented in the clinical study report.

Study enrollment commenced under Protocol VMNHU-003/C. There were 7 subjects enrolled under protocol version C, 5 enrolled under version E, 16 enrolled under version F, and 16 enrolled under version G; no subjects were enrolled under protocol version D, H or I.

Protocol VMNHU-003/E introduced the following changes to exclusion criteria in VMNHU-003/C:

- The study ulcer decreased by 50% or more at baseline from Screening (as assessed by comparison of post-debridement photos taken at Screening and Day 0); previously only ulcers that increased by 50% or more at baseline from Screening were excluded.
- Target ulcer located on an active (hot) Charcot foot; previously any Charcot foot was excluded.
- Body mass index (BMI) > 45 kg/m² at Screening; previously BMI > 35 kg/m² was excluded.
- All steroids except inhaled or ocular steroids; previously only high dose steroids were excluded.

Since these changes to the exclusion criteria were not expected to have a meaningful influence in favor of VM202 on the efficacy and safety parameters, no inferential analyses to account for the protocol version will be conducted. Descriptive summaries of the primary efficacy endpoint and overall adverse event rates will be produced for the subjects enrolled under different versions of the protocol.

Protocol VMNHU-003/F submitted with SAP revision C introduced the following changes to the inclusion criteria:

- the upper age limit for study participants will be raised to 80 years;
- addition of ABI > 1.4 (indicative of non-compressible vessels at the ankle) as a qualifying criterion for documented PAD;
- revision of 1 criterion for documented PAD to: history of lower extremity peripheral artery disease with previous related intervention in a leg.

Protocol VMNHU-003/G introduced the following changes to the exclusion criteria:

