9.5. Safety Analyses

No formal statistical testing will be conducted for the safety analyses. The following sections summarize the descriptive analysis presented for these safety endpoints. All subjects in the safety population will be included in these analyses, with subjects grouped by the actual treatment received. All summaries will be derived based on available data at scheduled visits; safety data at unscheduled visits will only be included in data listings. No imputation will be performed for missing values.

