9.5.2. Injection Site Adverse Events

The number and percentage of subjects with an injection site AE, by type (injection site reaction, ulceration, allergic reaction/hypersensitivity) and overall, will be summarized by treatment group at each weekly 'wound assessment and dressing change' visit and for the preand post-injection assessments on scheduled injection visit days (i.e., Days 0, 14, 28, and 42). The denominator for these percentages will be based on the number in the risk set following a given injection, which is the number of subjects who received that specific injection. The number and percentage of subjects for each grade within a given type of injection site AE will be summarized by treatment group at each assessment time point.

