9.5.3. Adverse Events

Adverse events will be collected once subjects meet all the study eligibility criteria and are randomized and administered study drug. However, all adverse event summaries will be restricted to Treatment-Emergent Adverse Events (TEAE), which are defined as those AEs that occurred after first dosing and those pre-existing conditions that worsened during the study. If the start time for an AE that occurs on the first date of dosing is unknown, then the event will be assumed to be a TEAE. If the start date of an AE is unknown, the event will be assumed to be a TEAE.

The number of subjects experiencing a particular event, the percentage of subjects experiencing the event, and the total number of events will be presented. The following summaries will be created:

- Overall summary of TEAEs, which includes the subject incidence of TEAEs and total number of unique TEAEs from each of the following AE summaries without regard to MedDRA system organ class or preferred term
- TEAE by SOC and preferred term
- TEAE by SOC and preferred term by injection number. Subjects and events are attributed to a given injection only if the event start date (subject to the missing date and

time imputation rules of Section 8.6.3) occurs on or after the date and time of that injection and not before the next injection.

- TEAE by SOC, preferred term and protocol version
- TEAE by SOC, preferred term and maximum severity. At the across-SOC and preferred term levels of subject summarization, a subject is classified according to the highest severity if the subject reported one or more events; severity within an SOC is not summarized. AEs with missing severity will be considered severe for this summary.
- TEAE by SOC, preferred term and closest relationship to study treatment (Related/Not Related). At each level of subject summarization, a subject is classified according to the closest relationship if the subject reported one or more events. AEs with a missing relationship will be considered 'related' for this summary; events classified as 'possibly', 'probably' or 'definitely' will be considered 'related'.

A listing of treatment-emergent SAEs (if any) will be provided, and if more than one occurs within any given preferred term, a summary of treatment-emergent SAEs by SOC and preferred term will be created.

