10. INTERIM ANALYSIS

Due to the early stopping of the study, the protocol-specified interim analysis will not be conducted.

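### Safety is to be judged against control, but the SAP's safety section plans no between-arm difference and no confidence interval, so with about 44 subjects equal rates or zero counts leave large excess risks open.

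*Protocol*

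**What the plan says.** Protocol 6.3.3 sets both the aim and the limit: "Safety analyses in this study will evaluate the safety profile of VM202, as compared with control. No formal statistical testing will be conducted". SAP 9.5 repeats that there will be no formal testing and continues: "The following sections summarize the descriptive analysis presented for these safety endpoints".

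The outputs that follow in SAP 9.5 are all by-arm summaries:

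- Adverse events (9.5.3): "The number of subjects experiencing a particular event, the percentage of subjects experiencing the event, and the total number of events will be presented". There are further splits by severity, relationship, injection number and protocol version.
- Injection-site events (9.5.2): numbers and percentages by type, grade and time point; the events by type "and overall, will be summarized by treatment group at each weekly" visit and at the injection visits.
- Vital signs and laboratory values (9.5.4, 9.5.5): descriptive values and changes from baseline, with shift tables for the laboratory values.
- Retinal fundoscopy (9.5.7): findings and changes by arm, described only.

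Elsewhere the SAP does give intervals. Wound closure gets a per-arm binomial interval and an interval for the difference (9.4.1.1, 9.4.1.2.2, 9.4.4.2). So do new ulcers on the target foot (9.4.4.5), which SAP 5.3.2 identifies from adverse event reports. Target-limb amputations, also taken from adverse event data, get log-rank and Kaplan-Meier analyses (9.4.4.6, 9.4.4.7). All of these sit under efficacy.

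On size, SAP section 1 reports: "There were 7 subjects enrolled under protocol version C, 5 enrolled under version E, 16 enrolled under version F, and 16 enrolled under version G", and none under versions D, H or I. SAP section 10 adds: "Due to the early stopping of the study, the protocol-specified interim analysis will not be conducted".

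**The concern.** The protocol says safety will be judged against placebo, and the SAP supplies the two columns but no estimate of the difference and no statement of how uncertain it is. At the planned 200 and 100 subjects that would have been a minor omission. At about 44 it matters, because two similar percentages, or two zeros, are easily read as showing that the arms are alike when the data cannot show this.

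At stake is the wording of the safety conclusion: similar to placebo on the one hand, or an excess of up to a stated number of points not excluded on the other. The SAP dropped the interim analysis because of the early stop, but its safety section says nothing about the reduced precision.

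**Working it through.** **Inputs.** Enrolled: 7 + 5 + 16 + 16 = 44 (SAP section 1). Allocation 2:1 (Protocol 3.4.7): 44 × 2/3 = 29.3 and 44 × 1/3 = 14.7, taken as 29 and 15. This split is an assumption. The safety population (SAP 7.2) needs at least one injection, so it could be smaller. Confidence level: two-sided 95% (SAP 9.1).

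**The plan's own figure.** The documents give no precision or detectable difference for safety. Their only sample-size figures are the efficacy powers for Fisher's test at 200 v 100. The lowest row (50% v 30%) is stated as 0.898. Exact enumeration, rejecting when either one-sided p ≤ 0.025, gives 0.897, so the planned size is understood correctly.

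**Zero events in one arm.** The Clopper-Pearson upper limit is 1 − 0.025^(1/n).

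- VM202: 1 − 0.025^(1/29) = 11.9%.
- Placebo: 1 − 0.025^(1/15) = 21.8%.
- At the planned sizes: 1.8% for n = 200 and 3.6% for n = 100.

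The chance of seeing no event at true risk p is (1 − p)^n. For 29 subjects, 0.95^29 = 22.6% at a 5% risk and 0.90^29 = 4.7% at a 10% risk.

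**Difference, D = x₁/29 − x₂/15.** The exact unconditional interval keeps each D that is not rejected when the tail probability of the score statistic is maximised over the unknown placebo rate. The last column spans two conventions: one two-sided 5% inversion, or two one-sided 2.5% inversions. All values are percentage points.

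| VM202 v placebo | Observed D | Score interval (Miettinen-Nurminen) | Exact unconditional, score-based |
|---|---|---|---|
| 0/29 v 0/15 | 0 | −20.8 to +11.9 | lower −22 to −23, upper +12.5 to +13.5 |
| 2/29 v 1/15 (6.9% v 6.7%) | +0.2 | −24.1 to +17.0 | lower −24 to −25, upper +17 to +18 |
| 4/29 v 2/15 (13.8% v 13.3%) | +0.5 | −26.3 to +20.8 | lower −27 to −28, upper +21 to +22 |
| 4/29 v 0/15 | +13.8 | −8.0 to +30.8 | lower −9 to −10, upper +31 to +32 |

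The rows use near-equal rates, because under 2:1 allocation equal counts are not equal rates (1/29 = 3.4%, 1/15 = 6.7%). In the zero-zero row, the upper limit on the VM202 excess comes mainly from the 29 VM202 subjects; the 15 placebo subjects mainly set the lower limit.

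**Sensitivity to the split.** At 30 v 14 the zero-zero score interval is −21.9 to +11.6, almost the same. At 200 v 100 it would have been −3.7 to +1.9.

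**Sensitivity to the method.** SAP 9.4.1.2.2 asks for an exact interval without saying which. Inverting the unstandardised difference instead of the score statistic gives about −30 to +30 for 4/29 v 2/15, and an upper limit of about +30 for zero-zero. The choice must therefore be written down.

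**Would testing help?** No. At 29 v 15, Fisher's test has only about 21% to 24% power for a 20-point excess when the placebo rate lies between 0% and 20%.

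**The case against.** Several points on the other side stand. Descriptive safety reporting without tests is a recognised choice, and a table by arm against concurrent placebo is itself a comparison, so no promise in Protocol 6.3.3 is broken. The numerators and arm sizes will be reported, so a reader could work out these intervals. The primary efficacy result is untouched.

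Stronger readings are tempting, and the documents do not support them:

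- A reader might infer that SAP 9.5 offers nothing but raw percentages. It also gives event totals, severity and relationship splits, shift tables and changes from baseline.
- A reader might infer that no harm is compared between arms. New target-foot ulcers and target-limb amputations, both drawn from adverse event data, are compared formally as exploratory efficacy endpoints.
- A reader might infer that the safety objective is itself worded as a comparison. Protocol 3.1 and SAP section 2 speak only of evaluating safety; the reference to control is in Protocol 6.3.3.
- A reader might blame the small placebo arm for the excess left open at zero counts. That limit depends mainly on the VM202 arm.
- A reader might infer that the plan intends to treat equal or zero counts as proof of no difference. No text says so; the misreading is a risk and not a stated rule.

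The availability of the counts does not fully answer the point. A list fixed in advance prevents a choice of events after the results are known, and puts the uncertainty beside the percentages.

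**Conclusion.** The point holds as a worthwhile, low-cost improvement. It is not an error in the decision to forgo testing. SAP 9.5 to 9.5.7 contains no between-arm difference and no interval for overall, related or serious adverse events, injection-site events or retinopathy, while the same SAP provides intervals for closure and for new ulcers.

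At about 29 v 15, zero events in both arms leaves a VM202 excess of about 12 to 13.5 points open, and near-equal rates of about 14% leave about −27 to +21 points open. These figures assume that all 44 enrolled subjects were randomized and dosed, and that the 2:1 ratio held. A move of one subject between arms changes them little; fewer dosed subjects would widen them. The counts in the table are illustrations and not trial results.

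**What to change.** Add a short paragraph to SAP 9.5 with a fixed list, counted per subject: any treatment-emergent adverse event, any related one, any serious adverse event, any injection-site adverse event, and new proliferative retinopathy. For each, report:

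1. the Clopper-Pearson 95% interval in each arm;
2. the VM202-minus-placebo difference with an exact unconditional 95% interval, stated to be by inversion of the score statistic, and whether one two-sided or two one-sided inversions are used;
3. where a count is zero, the upper limit in the text of the report.

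Label all of these descriptive and give no p-values, so the no-testing statement stands. For retinopathy, use as denominator the subjects who had the follow-up examination. If treatment codes are already open, say in the report that the intervals were added afterwards. Protocol 6.3.3 needs no change.

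The cost is a few lines of SAP text and a small amount of programming; no new data or visits are needed. The drawback is that the intervals will be wide and not adjusted for multiplicity, which the descriptive label should make plain.
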